# 6.2.2. IMP 2 - Cemiplimab

Based on data from ongoing long-term, accelerated, and stress stability studies, the cemiplimab IMP is considered stable for use.

Cemiplimab IMP must be stored at the trial centers at 2°C to 8°C. The temperature of storage in the refrigerator should be checked and recorded at least daily as prescribed in the Pharmacy Manual.

Details on storage and preparation for cemiplimab IMP for IV administration are provided in the Pharmacy Manual.

Storage of the infusion solution: cemiplimab IMP should be stored at room temperature ( $\leq 25^{\circ}$ C for no more than 8 h from the time of preparation to the end of infusion, or at 2°C to 8°C for no more than 24 h from the time of preparation to the end of infusion.

# 6.3. Measures to Minimize Bias: Randomization and Blinding

At screening, patients will be assigned a unique number (patient identification code), regardless of whether they actually receive trial treatment.

In Part 2, patients with mCRPC treated in Arm 1A or Arm 1B, and patients with LPC treated in Arm 2 or Arm 3, will be randomized in 1:1 ratio. Central randomization will be used to reduce potential investigator bias.

The site will contact the central randomization service prior to the start of trial treatment administration for each patient. The treatment assignment will be recorded on the applicable electronic case report form (eCRF), as required.

# **6.4.** Trial Treatment Compliance

Patients will receive trial treatment directly from the investigator or designee, under medical supervision. The date and time of each dose administered in the clinic will be recorded in the

CONFIDENTIAL Page 64 of 122

source documents and recorded in the eCRF. The dose of trial treatment and trial patient identification will be confirmed at the time of dosing by a member of the trial center staff other than the person administering the trial treatment.

# 6.5. Concomitant Therapy

Any background therapy for cancer or concomitant diseases/disorders not defined as NIMP and any non-drug cancer treatment (e.g., palliative radiotherapy/any supportive treatment) that is ongoing at the time of first IMPs administration (C1D1) or newly started after C1D1 is defined as concomitant treatment. Administration of concomitant treatment must be reported in the appropriate section of the eCRF.

Investigators may prescribe concomitant medications or treatments deemed necessary to provide adequate supportive care except for those medications identified as "prohibited" (Section 6.5.2).

- Palliative radiotherapy during the trial will be allowed for local pain control provided that (i) in the opinion of the investigator, the patient does not have PD AND (ii) no more than 10% of the patient's bone marrow is irradiated AND (iii) the radiation field does not encompass a target lesion.
- Granulocyte-colony stimulating factor and other hematopoietic growth factors may be used in the management of acute toxicity, such as febrile neutropenia, when clinically indicated or at the investigator's discretion.
- Blood cell transfusion is allowed during the trial if clinically indicated. No transfusion is allowed within 2 weeks prior to trial treatment initiation.
- Steroid treatment is permitted to modulate symptoms of an immune-related AEs at the discretion of the investigator. Replacement therapy (e.g., thyroxine, insulin, or physiologic corticosteroid replacement therapy for adrenal or pituitary insufficiency) is permitted. However, whenever possible corticosteroid treatment (prednisone >5 mg daily PO or IV, or equivalent) should be avoided as it counteracts with the MoA of the vaccine.
- Bisphosphonates (e.g., pamidronate, zoledronic acid, etc.) and denosumab.
- Multivitamins, vitamin D, calcium, and supplements in prevention of weight loss.
- For further details, please refer to the SoA: Section 1.3 (Part 1 and Part 2 Arms 1A and 1B), Section 1.4 (Part 2 Arms 2 and 3), and Section 1.5 (Part 2 Arm 1B [switch-over patients]).

# 6.5.1. Treatment of AEs Related to Treatment with BNT112 based on the RNA-LPX Class Profile

The class-intrinsic safety profile of RNA-LPX *per se* appears to be dominated by mild-to-moderate, transient and manageable influenza-like drug-related AEs (i.e., ADRs). The AEs are manageable by analgesics or antipyretics at recommended commonly used doses. Treatment of these events is dependent on the discretion of the treating physician with treatment suggestions provided below.

• Treat fever with acetaminophen or non-steroidal anti-inflammatory drugs (NSAIDs) with a dose per institution's recommendation.

CONFIDENTIAL Page 65 of 122

- After the first occurrence of influenza-like symptomatology, patients can be premedicated with standard therapeutic dose of acetaminophen, or NSAIDs, at least 60 minutes before BNT112 administration followed by a second dose 5 to 8 h after BNT112.
- Corticosteroid treatment (prednisone >5 mg daily PO or IV, or equivalent) should be avoided as either prophylaxis or treatment as it counteracts the effects of BNT112.
- Ensure adequate hydration of patients on the day of BNT112 administration. Consider administering IV isotonic fluid (e.g., normal saline 500 to 1000 mL) within approximately 1 h following the dose of BNT112 per institutional standard.

In addition to clinically manifested AEs described above, a transient reversible lymphopenia is mentioned above which was observed in laboratory examinations – there is no clinical manifestation of this event and no treatment required.

For further information about the known and potential risks of BNT112 refer to the latest version of the IB.

# 6.5.2. Prohibited Concomitant Therapy

The following concomitant therapies and medications are not allowed from C1D1 until the Safety Follow-Up (FU)-D30 visit (for Part 1 and Part 2 Arm 1B and Arm 3) and from C1D1 until Safety FU-D90 visit (for Part 2 Arm 1A, Arm 1B switch-over patients, and Arm 2):

- Any concomitant systemic anti-cancer therapy defined as any agent or combination of agents with clinically proven antineoplastic activity that achieves non-negligible systemic bioavailability after being administered by any route for affecting the malignancy, either directly or indirectly, including palliative and therapeutic objectives except for the concomitant use of cemiplimab (Part 2 Arms 1A and 2) and ADT (e.g., goserelin acetate) (Part 2 Arms 2 and 3).
- Immunosuppressive or maintenance therapy with systemic corticosteroids (PO or IV prednisone > 5 mg per day, or its equivalent) unless required per investigator's decision.
- Note: Replacement therapy (e.g., physiologic corticosteroid replacement therapy for adrenal or pituitary insufficiency) is not considered a form of systemic treatment and is permitted.
- Immunization with live-attenuated vaccines within 28 days prior to the first dose of IMP and during treatment with IMP. In addition, patients should not receive any live-attenuated vaccines within 3 months after the last dose of IMP.
- Use of herbal products that may decrease PSA levels (e.g., saw palmetto).

If a patient receives any of these during the trial, the sponsor must be notified for evaluation of whether the patient can continue treatment or not.

CONFIDENTIAL Page 66 of 122

#### 6.6. Dose Modifications

# 6.6.1. BNT112 (IMP/test product)

The DLs of BNT112 used in this trial include the 3 DLs for intra-individual patient dose titration (CCI and CCI µg) and 1 additional dose of CCI µg (with CCI µg of RNA of each antigen) which can be used for dose reduction in case of toxicities. A maximum of 2 subsequent dose reductions is allowed. Re-escalation to a higher dose level is not allowed.

For further information about the known and potential risks of BNT112 refer to the latest version of the IB.

# **6.6.1.1.** Dose-Limiting Toxicities – Part 1

For the purpose of intra-patient dose titration, TESAEs, TEAEs ≥Grade 3 and clinically significant abnormal lab values at least possibly related to BNT112 cancer vaccine will be collected and assessed for DLTs during the first cycle (21 days) of the dose titration part (DLT observation period). NCI CTCAE v.5.0 will be used to grade the intensity of TEAEs. At the discretion of the investigator, the dose of BNT112 cancer vaccine may be maintained at the current DL for one dose, i.e., intra-patient dose titration may be delayed. For these patients, the DLT assessment period is extended to 28 days.

#### DLT criteria are defined below:

• Any TEAE of Grade 5 intensity.

# Hematological

- Grade 3 and 4 febrile neutropenia (i.e., ANC  $<1.0 \times 10^9$  cells/L with a single temperature of >38.3°C or a sustained temperature of  $\ge 38$ °C for more than 1 h).
- Grade 4 thrombocytopenia ( $<25.0 \times 10^9$  platelets/L) for minimal duration of 7 days.
- Grade 3 and 4 hemorrhage associated with thrombocytopenia of Grade  $\geq 3$ .
- Grade 4 anemia.

#### Non-hematological

- Grade 4 cytokine release syndrome (CRS) according to Lee et al. 2019 (also refer to Table 10-5).
- Grade 3 CRS according to Lee et al. 2019 (also refer to Table 10-5), which has NOT improved to Grade 1 or resolved within 48 h.
- Any Grade ≥3 non-hematological TEAE at least possibly related which occurs during the first BNT112 cancer vaccine treatment cycle excluding:
  - Grade 3 CRS according to Lee et al. 2019 (refer to Table 10-5) which has improved to Grade 1 or resolved within 48 h.
  - Grade 3 fever (>40.0°C for <24 h).

  - Grade 3 hypotension (resolving within 24 h).
  - Related Grade 3 hypertension resolving within 24 h and considered as not clinically significant by the SRC.

CONFIDENTIAL Page 67 of 122

- Grade 3 infusion-related reactions that resolve to Grade ≤1 within 24 h.
- Non-hematological laboratory abnormalities that have no clinical consequences and resolve to Grade ≤2 within 14 days (this also includes electrolyte abnormalities that respond to medical intervention).
- Grade 3 diarrhea that responds to optimal antidiarrheal treatment within 3 days.
- Grade 3 vomiting that responds to optimal antiemetic treatment within 3 days.
- Grade 3 nausea that responds to optimal antiemetic treatment within 7 days.
- Grade 3 fatigue/asthenia when fatigue/asthenia was present at baseline or that lasts for
   4 days after the last administration of BNT112 cancer vaccine.
- Grade 3 irTEAEs that improve to Grade ≤1 in <7 days by appropriate care or with corticosteroids.
- Any related Grade 3 AE resolving within 24 h and considered as not clinically significant by the SRC.

All patients will be closely monitored for TEAEs during the DLT assessment period of Part 1.

TEAEs fulfilling the DLT criteria must be reported to the sponsor within 24 h as described in Section 10.3.3.

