#### 6.6.1.2. Handling of TEAEs

Administration of BNT112 may be delayed for up to 21 days at the discretion of the investigator in order to adequately manage TEAEs.

TEAEs that fulfill the DLT criteria both within and outside the DLT period should be handled as shown in Figure 6-2.

Grade 4 TEAEs fulfilling DLT criteria will always lead to BNT112 cancer vaccine discontinuation.

First occurrence of a TEAE of CTCAE Grade 3 fulfilling the DLT criteria:

- Investigator must contact the sponsor's medical monitor (MM) for thorough discussion in order to decide whether the patient should be withdrawn from BNT112 treatment or the next BNT112 dosing should be delayed.
- Administration of BNT112 can be delayed for up to 21 days (i.e., 1 cycle) unless otherwise approved by the sponsor's MM. If the intensity resolves to Grade ≤1 or baseline within this period, re-treatment may be considered under the following condition:
  - Sponsor and investigator will discuss any safety concerns in order to decide whether the next dose of BNT112 should be administered at the same DL or 1 DL below the current dose (i.e., 1 DL below the level of DLT occurrence: DL-1). In case investigator and sponsor disagree, the SRC must be consulted.

Second occurrence in the same patient of an identical TEAE of CTCAE Grade 3 after reexposure to BNT112:

• If re-treatment leads to an identical TEAE with same intensity, the next administration of BNT112 can be delayed for up to 21 days unless otherwise approved by the sponsor's

CONFIDENTIAL Page 68 of 122

MM. If the intensity of the TEAE resolves to Grade  $\leq 1$  or baseline within this period, retreatment may be considered under the following conditions:

Next dose of BNT112 should be administered 1 DL below the level of TEAE recurrence (DL-1 or DL-2).

Third occurrence of an identical TEAE of Grade ≥2 after re-exposure to BNT112:

• If re-treatment at a lower dose leads to a third identical TEAE with intensity Grade ≥2, the patient must permanently discontinue BNT112 treatment. No dose delay is allowed.

See Figure 6-2 for a decision tree for possible dose reductions and dosing delays required for TEAEs that fulfill the DLT criteria both within the DLT period and outside the DLT period.

[figure not shown]

Figure 6-2: Handling of TEAEs fulfilling the DLT criteria

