#### Please note:

- Re-escalation of BNT112 dose is not allowed for patients that previously have been dose-reduced based on investigator's, sponsor's, and SRC's decision.
- BNT112 must be permanently discontinued if the patient experiences an AE fulfilling the DLT criteria during any period of the trial even if outside the DLT period that fails to

CONFIDENTIAL Page 69 of 122

resolve to Grade  $\leq 1$  within 21 days after the planned dosing date unless otherwise approved by the sponsor's MM.

- BNT112 must be permanently discontinued if > 2 dose reductions are required.
- BNT112 must be permanently discontinued in case of a dose delay of > 21 days due to toxicity possibly related to BNT112 unless otherwise approved by the sponsor MM.

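### The general non-hematological DLT criterion is limited to Cycle 1, yet Section 6.6.1.2 relies on the DLT criteria to manage BNT112 throughout treatment

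*Protocol*

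**What the plan says.** The opening paragraph of Section 6.6.1.1 (Protocol) sets the counting window. Events are "assessed for DLTs during the first cycle (21 days) of the dose titration part (DLT observation period"). If titration is held back for one dose, the window is longer: "For these patients, the DLT assessment period is extended to 28 days".

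The criteria follow. The last non-hematological item is the general one, and it carries its own time limit: "Any Grade ≥3 non-hematological TEAE at least possibly related which occurs during the first BNT112 cancer vaccine treatment cycle excluding" a list of exceptions.

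Section 6.6.1.2 turns the criteria into dosing rules. Its scope sentence reads "TEAEs that fulfill the DLT criteria both within and outside the DLT period should be handled as" Figure 6-2 shows. Three rules then depend on the criteria being met:

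- **Grade 4:** "Grade 4 TEAEs fulfilling DLT criteria will always lead to BNT112 cancer vaccine" discontinuation.
- **Grade 3:** "First occurrence of a TEAE of CTCAE Grade 3 fulfilling the DLT criteria" requires contact with the medical monitor, a withdraw-or-delay decision, recovery to Grade 1 or baseline before re-treatment, and a decision on whether to step down one dose level.
- **Non-resolution:** the notes after the figure require permanent discontinuation, unless the medical monitor approves otherwise, for "an AE fulfilling the DLT criteria during any period of the trial even if outside the DLT period" that does not settle to Grade 1 or lower within 21 days of the planned dosing date.

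**The concern.** A DLT definition for a cohort decision needs a time window. A list of events that governs dosing for as long as the patient is treated must not have one. This protocol uses one list for both purposes and leaves the window inside its broadest item.

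At stake is consistent handling of serious related toxicity in a first-in-human trial. Section 2.3 says the risk of on-target, off-tumor toxicity cannot be deduced from the other RNA-LPX trials, although the sponsor rates it low. Such events could plausibly be non-hematological and appear after Cycle 1; that is an inference, not a documented rate. Two sites could handle the same Grade 4 event differently, one stopping BNT112 and one delaying it, and each could cite the protocol.

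**Working it through.** No power or error-rate calculation applies. The check compares the wording of each criterion with the wording that triggers each handling rule, then counts exposure.

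**Step 1. Which criteria carry a cycle limit (Section 6.6.1.1)?**

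| Group | Criteria | With a cycle limit |
|---|---|---|
| Grade 5 event | 1 | 0 |
| Hematological (febrile neutropenia, thrombocytopenia, hemorrhage with thrombocytopenia, anemia) | 4 | 0 |
| CRS (Grade 4; Grade 3 not improved within 48 h) | 2 | 0 |
| General related Grade 3 or higher non-hematological event | 1 | 1 |
| Total | 8 | 1 |

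Seven criteria can be met at any time. The eighth, which alone covers non-hematological events other than CRS or death, cannot be met after Cycle 1.

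**Step 2. Does the scope sentence in Section 6.6.1.2 cancel the limit?** Not by itself. Its extension beyond the DLT period keeps a full meaning through the seven unlimited criteria. It lifts the observation window; it does not rewrite a condition that is part of what the event is.

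**Step 3. Apply the rules to one example.** Take a related Grade 4 neurological event. In Cycle 1 it meets the general criterion and BNT112 stops. In Cycle 4 it meets none of the eight, so the Grade 4 rule is not triggered. A first Grade 3 event of the same kind likewise escapes the medical-monitor step and the non-resolution stop. Section 6.6.2 does not fill the gap, because its organ-specific rules concern cemiplimab.

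**Step 4. How much dosing falls after Cycle 1?** Section 6 plans three BNT112 doses in C1, three in C2 and one per cycle from C3. For treatment through cycle c (c at least 2), total doses = 6 + (c − 2), and doses after Cycle 1 = total − 3.

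| Treated through | Total doses | After Cycle 1 | Share |
|---|---|---|---|
| C2 | 6 | 3 | 50% |
| C3 | 7 | 4 | 57% |
| C8 (full LPC course) | 12 | 9 | 75% |
| C12 (mCRPC example) | 16 | 13 | 81% |

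**Step 5. Is the phrase consistent with the extended window?** A cycle is defined as 21 days. For a patient with delayed titration, 28 − 21 = 7 days, or 7/28 = 25% of the DLT period, lie inside the window but outside the first cycle. Literally, the general criterion cannot be met on days 22 to 28.

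**The case against.** The strongest reply is that this is an ambiguity rather than a gap. The opening of Section 6.6.1.1 confines DLT assessment of the whole list to the first cycle, and Section 6.6.1.2 then expressly lifts that window. If the phrase in the general criterion merely repeats the window, it is lifted too. The intent can indeed be inferred this way. But the phrase is redundant only for the cohort count. As part of the event definition it still operates, and only one of the eight items has it.

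Second, patients are not unprotected, which is correct:

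- For any TEAE, "Administration of BNT112 may be delayed for up to 21 days at the discretion of the investigator".
- BNT112 must stop if a delay for possibly related toxicity exceeds 21 days (unless the medical monitor approves otherwise), or if more than two dose reductions are needed.
- The second- and third-occurrence rules do not repeat the DLT condition, so recurrence of an event that qualified in Cycle 1 is arguably covered.
- Section 7.1 requires withdrawal for unacceptable toxicity, which it does not define.
- Section 8 asks for prompt discussion of immediate safety concerns with the sponsor. Most Grade 4 events would also be SAEs, reportable within 24 hours, and the SRC meets at least every three months.

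These narrow the consequence. None restores the automatic Grade 4 stop or the fixed sequence for a first Grade 3 event.

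Third, Figure 6-2 is not visible in the text available for review and might settle the matter. That cannot be checked; its title and the sentence referring to it both tie it to events that meet the DLT criteria.

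Fourth, Part 1 is fully enrolled with 9 patients dosed and was reviewed by the SRC on 17 May 2021, so days 22 to 28 no longer affect a cohort decision. That stands; the point shows only that the wording conflicts with the window.

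**Conclusion.** The concern holds. Followed as written, Section 6.6.1.2 omits its main mandatory steps for a first related Grade 3 or 4 non-hematological event, other than CRS, that occurs after Cycle 1. What remains is largely discretionary. This should be fixed, but it is a partly mitigated drafting conflict: no endpoint, sample size or expansion-dose decision depends on it.

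The conclusion rests on a literal reading of the criterion and on Figure 6-2 not overriding it. The dose shares describe the schedule, not risk. SAP Sections 5 and 8.7.6 record that mCRPC enrollment was stopped after the interim analysis, before LPC enrollment was complete. The point therefore concerns the LPC arms and any mCRPC patient still receiving BNT112.

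**What to change.** Delete the words that confine the general non-hematological criterion to the first BNT112 cycle. Keep the counting window only in the opening paragraph of Section 6.6.1.1, as 21 days, or 28 days when titration is delayed. The alternative is one sentence in Section 6.6.1.2 stating that the event list applies by type and grade in every cycle. Figure 6-2 should be checked for agreement.

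The cost is a one-line protocol clarification and a letter to sites. It needs no new data, visits or patients, and the Part 1 cohort rule keeps its stated window.

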#### 6.6.1.2. Handling of TEAEs

Administration of BNT112 may be delayed for up to 21 days at the discretion of the investigator in order to adequately manage TEAEs.

TEAEs that fulfill the DLT criteria both within and outside the DLT period should be handled as shown in Figure 6-2.

Grade 4 TEAEs fulfilling DLT criteria will always lead to BNT112 cancer vaccine discontinuation.

First occurrence of a TEAE of CTCAE Grade 3 fulfilling the DLT criteria:

- Investigator must contact the sponsor's medical monitor (MM) for thorough discussion in order to decide whether the patient should be withdrawn from BNT112 treatment or the next BNT112 dosing should be delayed.
- Administration of BNT112 can be delayed for up to 21 days (i.e., 1 cycle) unless otherwise approved by the sponsor's MM. If the intensity resolves to Grade ≤1 or baseline within this period, re-treatment may be considered under the following condition:
  - Sponsor and investigator will discuss any safety concerns in order to decide whether the next dose of BNT112 should be administered at the same DL or 1 DL below the current dose (i.e., 1 DL below the level of DLT occurrence: DL-1). In case investigator and sponsor disagree, the SRC must be consulted.

Second occurrence in the same patient of an identical TEAE of CTCAE Grade 3 after reexposure to BNT112:

• If re-treatment leads to an identical TEAE with same intensity, the next administration of BNT112 can be delayed for up to 21 days unless otherwise approved by the sponsor's

CONFIDENTIAL Page 68 of 122

MM. If the intensity of the TEAE resolves to Grade  $\leq 1$  or baseline within this period, retreatment may be considered under the following conditions:

Next dose of BNT112 should be administered 1 DL below the level of TEAE recurrence (DL-1 or DL-2).

Third occurrence of an identical TEAE of Grade ≥2 after re-exposure to BNT112:

• If re-treatment at a lower dose leads to a third identical TEAE with intensity Grade ≥2, the patient must permanently discontinue BNT112 treatment. No dose delay is allowed.

See Figure 6-2 for a decision tree for possible dose reductions and dosing delays required for TEAEs that fulfill the DLT criteria both within the DLT period and outside the DLT period.

[figure not shown]

Figure 6-2: Handling of TEAEs fulfilling the DLT criteria

